#### 4.5 Duration of Therapy

In the absence of treatment delays due to AEs, treatment may continue until the end of study-defined treatment or until:

- Disease progression (Note: treatment may continue until progression is confirmed by repeat scan approximately 6 weeks later to rule out pseudoprogression based on investigator discretion)
- Inter-current illness that prevents further administration of treatment
- Unacceptable toxicity
- Pregnancy
- Patient decides to withdraw from study treatment, **OR**
- General or specific changes in the patient's condition render the patient unacceptable for further treatment in the judgment of the investigator.

#### 4.6 Duration of Follow Up

After stopping study therapy, subjects should be followed as described in the time and events table in Section 6.0 and in the follow up section in 6.5. After two years of follow-up as described in the time and events tables, subsequent follow-up will be per standard of care. Subjects can be contacted by phone or followed via medical records every 3 months (+/- 15 days) for follow up information on disease progression and survival until death.

#### 4.7 Removal of Patients from Protocol Therapy

Patients will be removed from protocol therapy and the PI notified when any of the criteria listed in section 4.5 apply. The reason for discontinuation of protocol therapy will be documented on the eCRF.

In case a patient decides to prematurely discontinue protocol therapy (“refuses treatment”), the patient should be asked if she or he may still be contacted for further scheduled study assessments or have relevant information on PFS and OS accessed from their medical record. The outcome of that discussion should be documented in both the medical records and in the eCRF.

Excessive patient withdrawals from protocol therapy or from the study can render the study un-interpretable; therefore, unnecessary withdrawal of patients should be avoided.

#### 4.8 Study Withdrawal

If a patient decides to withdraw from the study (and not just from protocol therapy) all efforts should be made to complete and report study assessments as thoroughly as possible. The investigator should contact the patient or a responsible relative by telephone or through a personal visit to establish as completely as possible the reason for the study withdrawal. A complete final evaluation at the time of the patient's study withdrawal should be made with an explanation of why the patient is withdrawing from the study. If the reason for removal of a patient from the study is an adverse event, the principal specific event will be recorded on the eCRF.

### 5.0 DRUG INFORMATION

#### 5.1 Talimogene Laherparepvec (Imlygic™)

Please refer to the Talimogene laherparepvec pharmacy information guide for additional information.

##### 5.1.1 Description

Talimogene laherparepvec is a sterile suspension of live, attenuated herpes-simplex virus -1 (HSV-1) that has been genetically modified to express huGM-CSF. The parental virus for talimogene laherparepvec was a primary isolate, which was subsequently altered using recombinant methods to result in gene deletions and insertions.

##### 5.1.2 Supplier/How Supplied

Talimogene laherparepvec will be presented as a sterile, semi-translucent to opaque solution for injection (opacity is different for each concentration) preservative-free frozen liquid in a single use 2 mL cyclic olefin polymer (COP) plastic resin vial. Each vial will contain talimogene laherparepvec at a nominal concentration of  $10^6$  PFU/mL or  $10^8$  PFU/mL in an aqueous sodium phosphate buffer with sodium chloride, sorbitol and myo-inositol added as stabilizers and water for injection (WFI). Vials are appropriately filled to ensure that a sufficient deliverable dose is provided. Each 2 mL vial will contain approximately 1.15 mL of talimogene laherparepvec with a 1.0 mL deliverable volume. Each vial is intended for single use only.

Vials will be sealed with gray rubber stoppers, fluorotec-coated on the product side. The vial caps will be color coded and may be used to help distinguish between the  $10^6$  PFU/mL and  $10^8$  PFU/mL vial concentrations. The supply for  $10^6$  PFU/mL vials will be packaged separately from the supply for the  $10^8$  PFU/mL vials.

- The  $10^6$  PFU/mL strength is supplied in a box containing 10 vials.
- The  $10^8$  PFU/mL strength is supplied in a box containing 20 vials.

For additional information please refer to the talimogene laherparepvec pharmacy information guide.

### 5.1.3 Storage, Handling and Dispensing

Talimogene laherparepvec must be stored in a non-cycling freezer maintained at a set point of -80°C in a secured location until planned use. Cycling, frost-free, auto defrost freezers must not be used since they cycle to warmer temperatures several times a day. Vials should be kept within the secondary container to protect from light. The table below outlines the storage temperature requirements.

Storage of Talimogene Laherparepvec - Freezer Set Point

Freezer Set Point (°C)	Acceptable Variation	Acceptable Range
-80°C	± 10°C	-90°C to -70°C

All infusions of talimogene laherparepvec will be in 200cc NS followed by injection of 20cc sterile saline to clear the catheter. Subjects will be instructed to allow the product to dwell for at least 24 hours after which they should next drain the catheter when next needed to palliate shortness of breath, consistent with standard of care use of the catheter. Subjects or their caregivers will be instructed to use medical gloves when draining the catheter and to avoid physical contact with fluid drained from the catheter. Standard drainage bottles will be used. Subjects will be allowed to either add bleach to the 60 cc syringe or bottle and then dispose per standard procedures or return to the investigators for disposal. These precautions will be advised permanently after study initiation (See [Appendix D - Information Sheet for Caregivers, Family Members or other Close Contacts to Clinical Trial Participants being given Talimogene Laherparepvec](#)).

### 5.1.4 Preparation

All personnel handling talimogene laherparepvec or material contaminated with talimogene laherparepvec must observe institutional safety precautions.

Preparation to occur in biological safety cabinet per institutional guidelines.

Clean talimogene laherparepvec vial stopper with an alcohol swab.

Withdraw 1ml from each of 4 vials, using a sterile 18-26 gauge disposable needle, for a total volume of 4ml.

**For additional information please refer to the talimogene laherparepvec pharmacy manual.**

### 5.1.5 Return and Retention

The investigator is responsible for keeping accurate records of the clinical supplies received from Amgen, Inc. or designee, the amount dispensed to the subjects and the amount remaining at the conclusion of the trial.

Upon completion or termination of the study, all unused and/or partially used investigational product will be destroyed at the site per institutional policy (e.g., UNC IDS drug destruction policy). It is the Investigator's responsibility to arrange for disposal of all empty containers, provided that procedures for proper disposal have been established according to applicable federal, state, local and institutional guidelines and procedures, and provided that appropriate records of disposal are kept.

### 5.1.6 Warnings and Precautions (talimogene laherparepvec)

#### Accidental Exposure

Accidental exposure may lead to transmission of herpetic infection. Healthcare providers who are immunocompromised or pregnant should not administer talimogene laherparepvec. Protective clothing and gloves should be worn during preparation and administration of talimogene laherparepvec.

#### Herpetic Infection

Herpetic infections have been reported in patients treated with talimogene laherparepvec. Healthcare providers exposed to talimogene laherparepvec are encouraged to report suspected herpetic infections as well. Disseminated herpetic infection may also occur in immunocompromised patients. Patients who develop suspicious herpes-like lesions should follow standard hygienic practices to prevent viral transmission. Suspected herpetic lesions should be reported to Amgen at [name]; patient or close contacts have the option of follow-up testing for further characterization of infection. Healthcare providers exposed to talimogene laherparepvec are encouraged to report the suspected herpetic infections to Amgen at [name]. Talimogene laherparepvec is sensitive to acyclovir.

Please see section 11.4 [Appendix D: Information sheet for caregivers, family members or other close contacts to clinical trial participants being given talimogene laherparepvec](#).

#### Immune-mediated events

Talimogene laherparepvec may result in immune-mediated events including glomerulonephritis, vasculitis, pneumonitis, worsening of psoriasis, and vitiligo.

Common adverse events ( $\geq 25\%$ ) in talimogene laherparepvec-treated patients were fatigue, chills, pyrexia, nausea, influenza-like illness, and injection site pain.

Please refer to **the talimogene laherparepvec investigators brochure** for additional information on identified and potential risks.

## 5.2 Additional important Nivolumab (Opdivo®)

See the prescribing information for Opdivo® (Nivolumab) at [http://packageinserts.bms.com/pi/pi\\_opdivo.pdf](http://packageinserts.bms.com/pi/pi_opdivo.pdf) for more detailed information.

### 5.2.1 Description

Nivolumab injection drug product is a sterile, non-pyrogenic, single-use, isotonic aqueous solution formulated at 10mg/10 mL. The vials supplied contain 100 mg. Nivolumab is a sterile, preservative-free, non-pyrogenic clear to opalescent, colorless to pale-yellow liquid that may contain light (few) particles for IV administration. Nivolumab will be administered as standard of care following the institutional guidelines.

### 5.2.2 Packaging and Labeling

Primary Packaging (Volume)/Label type: Carton of 5 or 10 vials  
Secondary Packaging (Qty)/Label type: 10-cc Type 1 flint glass vials stoppered with butyl stoppers and sealed with aluminum seals.

### 5.2.3 Storage and Handling

Store nivolumab under refrigeration at 2°C to 8°C (36°F-46°F) in the original package until time of use. Protect from light and freezing. Do not shake the vial.

If stored in a glass front refrigerator, vials should be stored in the carton. Recommended safety measures for preparation and handling of nivolumab include laboratory coats and gloves.

### 5.2.4 Dose, Schedule and Administration

See section 4.3.2

Nivolumab will be given every two weeks at a dose of 240 mg to be administered as a 30 minute IV infusion.

Subjects may be dosed no less than 12 days from the previous dose of drug. There are no premedications recommended for nivolumab on the first cycle.

Subjects should be carefully monitored for infusion reactions during nivolumab administration. If an acute infusion reaction is noted, subjects should be managed according to institutional guidelines (See section 4.3.3).

Doses of nivolumab may be interrupted, delayed, or discontinued depending on how well the subject tolerates the treatment.

### 5.2.5 Preparation

Follow institutional guidelines for Nivolumab preparation or see the nivolumab prescribing information for preparation instructions. Nivolumab Injection, 100 mg/10 mL (10 mg/mL) is to be administered as an IV infusion through a 0.2-micron

to 1.2-micron pore size, low-protein binding polyether sulfone (PES) membrane in-line filter at the protocol-specified dose. It is not to be administered as an IV push or bolus injection. Nivolumab injection can be infused undiluted (10 mg/mL) or diluted with 0.9% Sodium Chloride Injection, USP or 5% Dextrose Injection, USP to protein concentrations as low as 1 mg/mL. Care must be taken to assure sterility of the prepared solution as the product does not contain any antimicrobial preservative or bacteriostatic agent.

#### 5.2.6 Stability

Nivolumab solution for injection can be stored after preparation at room temperature for no more than 4 hours. This includes room temperature storage of the infusion in the IV container and time for administration of the infusion OR under refrigeration at 2°C to 8°C (36°F-46°F) for no more than 24 hours from the time of infusion preparation.

#### 5.2.7 Return and Retention of Nivolumab

Partially used and completely used vials will be destroyed per institutional guidelines.

#### 5.2.8 Adverse Events Associated with Nivolumab

The adverse events listed below have been reported in patients receiving nivolumab. See section 4.3 for further instruction on the management adverse events associated with nivolumab therapy.

- Immune-mediated pneumonitis: Defined as requiring use of corticosteroids and no clear alternate etiology, including fatal cases have occurred with nivolumab treatment.
- Immune-mediated colitis: Defined as requiring use of corticosteroids and no clear alternate etiology, including fatal cases have occurred with nivolumab treatment.
- Immune-mediated hepatitis: Defined as requiring use of corticosteroids and no clear alternate etiology have occurred with nivolumab treatment.
- Immune-mediated endocrinopathies: Hypophysitis, adrenal insufficiency, hypo- and hyper-thyroidism, and type I diabetes mellitus have occurred with nivolumab treatment.
- Immune-mediated nephritis and renal dysfunction: Defined as renal dysfunction or  $\geq$ Grade 2 increased creatinine, requirement for corticosteroids, and no clear alternate etiology, can occur with nivolumab treatment.
- Immune-mediated rash: Severe rash (including rare cases of fatal toxic epidermal necrolysis) can occur with nivolumab treatment.
- Immune-mediated encephalitis: Withhold nivolumab in patients with new-onset moderate to severe neurologic signs or symptoms.
- Other immune-mediated adverse reactions: Monitor for as described in 4.3.2.

- Complications of allogeneic human stem cell transplant after nivolumab: Monitor for hyper acute graft-versus-host disease (GVHD). Transplant related mortality has occurred.
- Infusion reactions: Severe infusion reactions have been reported in <1.0% of patients in clinical trials of nivolumab. See section 4.3.3 for information on the management of nivolumab-related infusion reactions.

#### 5.2.9 Use in Pregnancy

If a patient inadvertently becomes pregnant while on treatment with nivolumab, the patient will immediately be removed from the study. The site will contact the patient at least monthly and document the patient's status until the pregnancy has been completed or terminated.

#### 5.2.10 Use in Nursing Women

It is unknown whether nivolumab is excreted in human milk. Since many drugs are excreted in human milk, and because of the potential for serious adverse reactions in the nursing infant, patients who are breast-feeding are not eligible for enrollment.

## 6.0 Evaluations and Assessments

### 6.1 Safety Run-in Cohort 1 (Talimogene Laherparepvec Only)

Assessments	Pre-Study 	Treatment Period  Cycle 1 is 3 weeks in length, subsequent cycles are Q2W							Follow up	
		Cycle 1 Day 1 	Cycle 1 Day 8	Cycle 2 Day 1	Cycle 2 Day 8	Cycle 3 Day 1	Cycle 4 Day 1	Cycle 5 - 9 Day 1	End of TXT 	Long Term FU 
Informed Consent	X									
HSV-1 antibody	X									
History 	X	X	X	X	X	X	X	X	X	X
Physical exam 	X	X	X	X	X	X	X	X	X	
Performance Status	X	X	X	X	X	X	X	X	X	
EKG	X						X			
Troponin	X						X			
Chest X-ray	X	As needed and/or after three consecutive drainages with $\leq 50$ cc drainage (every other day drainages) of pleural fluid drainage accompanied by patient-defined improvement in symptoms (cough, chest pain and/or dyspnea).							X	
Tumor measurement 	X							X 	X 	X
Pregnancy test 	X									
Hematology 	X 	X	X	X	X	X	X	X	X	
Serum chemistries 	X	X	X	X	X	X	X	X	X	
Liver function tests 	X	X	X	X	X	X	X	X	X	
Coagulation 	X									
Toxicity Assessment	X	X	X	X	X	X	X	X	X	X
Concomitant Meds	X	X	X	X	X	X	X	X	X	
talimogene laherparepvec IP Q3W 10  PFU		X								
talimogene laherparepvec IP Q2W 10  PFU				X		X	X	X		

Assessments	Pre-Study 	Treatment Period  Cycle 1 is 3 weeks in length, subsequent cycles are Q2W							Follow up	
		Cycle 1 Day 1 	Cycle 1 Day 8	Cycle 2 Day 1	Cycle 2 Day 8	Cycle 3 Day 1	Cycle 4 Day 1	Cycle 5 - 9 Day 1	End of TXT 	Long Term FU 
Patient Diary 		X	X	X	X	X	X	X	X	
Blood / urine / pleura samples to assess viral shedding		X 	X 	X 	X 	X 	X 		X 	
Blood sample for correlative studies 		X		X			X		X	
Tumor biopsy	X 									
Collection of pleural drainage 		X		X					X	
Buccal Swab	X 	X 								
Modified Borg 		X		X			X		X	
Survival analysis										X

### Key to Time and Events Table Footnotes

1. Radiological assessments, EKG and physical exam may be performed up to 4 weeks prior to day 1 of treatment. Other evaluations except for pregnancy must be performed within 2 weeks prior to Cycle 1 Day 1 of treatment. Serum B-HCG must be performed within 72 hours prior to first dose of study medication for women of child-bearing potential. Screening labs performed within 72 hours prior to Cycle 1 Day 1 do not need to be repeated on C1D1.
2. The first treatment cycle with talimogene laherparepvec is 3 weeks (21 days) in length to allow for seroconversion (See Schema in 4.1). Subsequent treatment cycles are to be repeated every 2 weeks (14 days) X 8 cycles or until progression, whichever occurs first. **A window of +/- 2 days applies to all study visits within the treatment period.**
3. The end of treatment/safety follow up visit should only occur when patients permanently stop study treatment and should be performed 30 days (+/-7 days) after the last dose of study medication. Patients who have an ongoing  $\geq$ grade 2 or serious AE (SAE) at this visit will continue to be followed until the event is resolved or deemed irreversible by the investigator. Patients stopping talimogene laherparepvec should be monitored for at least 30 days for emerging AEs after discontinuing the drug. After two years of follow-up per standard of care (Q3 months +/- 15 days) as outlined in the time and events table, subsequent follow up will be by phone contact or via medical records to document disease progression and survival information until death (Q3 months +/- 15 days).
4. Complete history at baseline only (to include smoking history), thereafter focused history on symptoms/toxicity; physical exam to include height (baseline only), examination of the skin, weight, pulse oximetry, and vital signs.
5. Tumor imaging should remain consistent throughout study and performed at baseline, just prior to D1 of cycle 5, at progression or the end of treatment (i.e. completion of cycle 9), and should include those thought by investigator to best capture status of disease. Examples include PET, contrasted computed tomography (CT) of the chest, abdomen and pelvis, and bone scan. Imaging following completion of study procedures should be per standard of care for the relevant disease state.
6. Hematology: CBC with differential and platelet count; Liver function tests: total bilirubin, direct bilirubin, AST (SGOT), ALT (SGPT), and alkaline phosphatase, direct bilirubin if indicated, at screening only. Serum chemistry: potassium, sodium, calcium, creatinine, chloride, glucose, magnesium, phosphorus, BUN, albumin, uric acid, and total protein.
7. Coagulation: PT or INR and PTT or aPTT
8. Patient drainage diary (See Appendix E in Section 11.5)
9. Collect urine, pleura and 5 mL of blood (lavender top EDTA tube) at each time point denoted below. Additional details on sample collection provided in the study laboratory manual.
  - C1D1: pre-dose, 1 hr post dose, 4 hrs post dose and 6 hrs post dose samples
  - Collect predose samples on C1D8/C2D1/C2D8/C3D1/C4D1 and at end of treatment
10. Blood samples will be collected for correlative studies (at pretreatment, 3 weeks post treatment, 9 weeks post treatment, and end of treatment according to lab manual.
11. Tumor biopsy will be collected for correlative studies. All subjects in this study will have had pleural catheter placed as standard of care, which will allow for fresh biopsy collection. If for some reason fresh biopsy cannot be collected, archival tumor will be accepted.
12. If feasible, Pleural fluid will be collected for correlative studies at the following time points: pre treatment, 3 weeks post treatment, 9 weeks post treatment, and end of treatment, according to the lab manual.
13. Modified Borg Rating of Perceived Dyspnea (MBS) will be used to assess level of exertion (Provided in 11.6 Appendix F: Borg Scale).
14. Buccal swab for matched normal genomic DNA
15. Repeat if insufficient sequencing.

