### 2.4.2 Secondary Endpoints

**2.4.2.1 Median PFS.** PFS will be defined as the time from D1 of treatment until death or progression.

**2.4.2.2 Median OS.** OS is defined as the time from D1 of treatment to death from any cause.

**2.4.2.3 Tumor response** will be defined as the proportion of patients with reduction in tumor (irCR+irPR) per irRECIST criteria outlined in section 6.8.

**2.4.2.4 Clinician assessed toxicity** will be classified and graded according to the National Cancer Institute's Common Terminology Criteria for Adverse Events (NCI-CTCAE, version 5.0).

**2.4.2.5 Use of modified Borg rating scale** for perceived dyspnea (10 point scale from 1 to 10 which measures perception of dyspnea) [59, 60] (Provided in 11.6 **Appendix F: Borg Scale**).

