- 3.2.2 Has had prior chemotherapy, targeted small molecule therapy, or radiation therapy within 2 weeks prior to study Day 1.
- 3.2.3 Has had a prior monoclonal antibody within 4 weeks prior to study Day 1, or who has not recovered to,  $\leq$  Grade 1 toxicity at baselines from adverse events due to agents administered more than 4 weeks earlier. Exceptions to these criteria may be allowed at the discretion of the investigator for toxicities that are not expected to be exacerbated by nivolumab or talimogene laherparepvec (e.g., alopecia, peripheral neuropathy, etc).
- 3.2.4 Any concurrent chemotherapy, IP, biologic or hormonal therapy for cancer treatment. Concurrent use of hormonal therapy for non-cancer-related conditions (e.g., hormone replacement therapy) is acceptable.
- 3.2.5 Major surgery within 28 days prior to day 1 of study treatment from which the patient has not completely recovered.
- 3.2.6 Has a diagnosis of immunodeficiency or is receiving systemic steroid therapy or any other form of immunosuppressive therapy within 7 days prior to the first dose of trial treatment.
- 3.2.7 Has a known secondary malignancy that is progressing or requires active treatment. Exceptions include basal cell carcinoma of the skin, squamous cell carcinoma of the skin, or in situ cervical cancer that has undergone potentially curative therapy.
- 3.2.8 Has an active automimmune disease requiring systemic treatment within the past 3 months or a documented history of clinically severe autoimmune disease, or a syndrome that requires systemic steroids or immunosuppressive agents; subjects with resolved childhood asthma/atopy would be an exception to this rule. Subjects that require intermittent use of bronchodilators or local steroid injections would not be excluded from the study. Subjects with hypothyroidism stable on hormone replacement or Sjorgen's syndrome will not be excluded from the study. Replacement therapy (e.g., thyroxine, insulin, or physiologic corticosteroid replacement therapy for adrenal or pituitary insufficiency, etc.) is not considered a form of systemic treatment. Subjects with vitiligo, Grave's disease, or psoriasis not requiring systemic treatment (within the past 2 years) are not excluded.
- 3.2.9 Has a history of non-infectious pneumonitis that required steroids; currently active non-infectious pneumonitis; or evidence of interstitial lung disease.
- 3.2.10 Has an active infection requiring systemic therapy or history of uncontrolled infection.

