### 6.3 Pre-Study Assessments for Safety Run in Cohorts and Phase II (Tables 6.1 and 6.2)

Screening evaluations are to be conducted within 2 weeks prior to start of protocol therapy. Scans for tumor evaluation must be done within 4 weeks prior to the start of therapy. (**Note:** Hematology and other lab parameters that are  $\leq$  grade 2 BUT still meet criteria for study entry are allowed. Furthermore, changes in laboratory parameters during the study should not be considered adverse events unless they meet criteria for dose modification(s) of study medication outlined by the protocol and/or worsen from baseline during therapy). Pre-study assessments include:

Complete medical history (including smoking history) and physical examination (including skin exam, height, and weight)

ECOG Performance Status (see appendix A)

Laboratory evaluations:

- CBC with differential
- Serum chemistries (potassium, sodium, calcium, creatinine, chloride, glucose, magnesium, phosphorus, BUN, albumin, uric acid, and total protein)
- Liver function tests (total bilirubin, direct bilirubin if indicated, alkaline phosphatase, AST, ALT)
- Troponin
- Serum pregnancy test in women of childbearing potential (Note: pregnancy test to be done within 72 hours of day 1 of treatment)
- Coagulation (PT/INR)
- HSV-1 antibody test
- Blood samples collected for correlative studies

EKG

Chest x-ray after thoracentesis (baseline)

Concomitant medication(s): All concomitant medications will be recorded.

Tumor evaluation: CT or MRI scan of the neck, results from physical examination head and neck, and chest imaging (x-ray or CT scan at discretion of physician)

Tumor biopsy: All subjects will have catheter placed per standard of care, therefore fresh biopsy should be easily accessible. If fresh biopsy is unavailable, archival will be accepted.

Toxicity evaluation: Use NCI CTCAEv5.0 for notation of any baseline toxicity  
Modified Borg Scale of Perceived Dyspnea (Provided in 11.6 Appendix F: Borg Scale): Scale ranging from 0 (no dyspnea) to 10, which evaluates perceived level of shortness of breath.

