**Definition of Response Using irRECIST**

**irComplete Response (irCR):** Complete disappearance of all lesions (whether measurable or not) and no new lesions. Lymph nodes must decrease to <10mm in short axis. Confirmation of a response is not mandatory. It is the judgment of the investigator whether a nonmeasurable radiographic nodule is likely cancerous; only nodules felt likely cancerous will preclude the judgement of irCR.

- **irPartial Response (irPR):** Decrease in tumor burden  $\geq 30\%$ , in total measured tumor burden relative to baseline, non-target lesions are irNN, and no unequivocal progression of new non-measurable lesions
- **irNon CR/Non-PD (irNN):** No target disease was identified at baseline and at follow up the patient fails to meet criteria for irCR or irPD.
- **irStable Disease (irSD):** Does not meet criteria for irCR or irPR, in the absence of irPD.
- **irProgressive Disease (irPD):** At least 20% and minimum 5 mm absolute increase in total measured tumor burden compared to nadir, or irPD for non-target or new on-measurable lesions. Confirmation of progression is recommended minimum of 4 weeks after the first irPD assessment.
- **Nonprogressive disease:** Measurable disease is not required for this study. Patients with CR at the time of study entry or otherwise nonmeasurable disease will be assessed for progression. In the event of PD, this should be noted. In the absence of meeting criteria for progression, nonprogressive disease should be coded (NPD).

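### A compliant baseline tumor scan can predate up to about 14 days of prior chemotherapy, targeted therapy or radiation, so shrinkage from that treatment can count toward the secondary irRECIST response rate and affect PFS

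*Combined protocol and SAP*

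**What the plan says.** **Imaging window.** Footnote 1 under the tables in 6.1 (cohort 1) and 6.2 (cohort 2 and expansion) reads "Radiological assessments, EKG and physical exam may be performed up to 4 weeks prior to day 1 of treatment". Section 6.3 agrees: "Scans for tumor evaluation must be done within 4 weeks prior to the start of therapy".

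**Washout.** Exclusion 3.2.2 applies to a patient who "Has had prior chemotherapy, targeted small molecule therapy, or radiation therapy within 2 weeks prior to study Day 1". The other classes are handled differently. Exclusion 3.2.3 covers a patient who "Has had a prior monoclonal antibody within 4 weeks prior to study Day 1", which matches the imaging window. Investigational agents (3.2.1) have at least 28 days. Exclusion 3.2.4 covers "Any concurrent chemotherapy, IP, biologic or hormonal therapy for cancer treatment" and gives no washout length.

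**Use of the baseline.** Section 6.8 defines irPR as a fall of at least 30% "in total measured tumor burden relative to baseline". It defines irPD as growth of at least 20%, with a 5 mm minimum "absolute increase in total measured tumor burden compared to nadir". Section 2.4.2.1 adds that "PFS will be defined as the time from D1 of treatment until death or progression". The first on-study scan comes before Cycle 5 Day 1.

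**The concern.** For the classes in 3.2.2, the imaging window is twice as long as the washout. A patient can be scanned on day −28, receive chemotherapy, a targeted drug or radiation until about day −15, start study treatment on Day 1, and break no rule. I found no requirement in 3.2, 6.1 to 6.3 or 6.8 that the scan follow the last prior treatment, or be repeated if treatment comes in between.

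Any shrinkage produced by that intervening treatment is then measured as change on virus plus nivolumab. Objectives 2.2.1 (PFS) and 2.2.3 (response rate) depend on these measurements. The trial has a single arm, so no control group carries the same bias. With 24 evaluable patients, one reclassified responder moves the response rate by 1/24 = 4.2 percentage points. Section 6.8 does not require measurable disease, so the number evaluable for response may be smaller and the shift larger.

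**Working it through.** The plan gives no figure for this gap, so there is none of its own to reproduce. The check is a comparison of windows followed by an illustration.

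**1. Overlap.** Imaging window: 28 days (footnote 1 in 6.1 and 6.2; section 6.3). Washout: 14 days (3.2.2). Maximum overlap = 28 − 14 = 14 days. For antibodies it is 28 − 28 = 0. For hormonal therapy no washout is stated, so the overlap has no stated limit short of Day 1.

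**2. Which scan is the reference.** Cycle 1 lasts 21 days and cycles 2 to 4 last 14 days each, so Cycle 5 Day 1 falls 21 + 3 × 14 = 63 days after Day 1. At the scan before that visit, the baseline is the only previous value. It is then the reference for irPR and also the nadir for irPD.

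**3. Effect of shrinkage before Day 1.** Set the baseline sum to 100 and let s be the fractional shrinkage caused by prior treatment between the scan and Day 1. The documents give no value for s; 5% to 20% is my assumption. The sum on Day 1 is 100(1 − s).

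- irPR is reached at 70. Further fall needed = 1 − 0.70/(1 − s).
- irPD at the first on-study scan is reached at 120. Growth needed from the Day 1 size = 1.20/(1 − s) − 1. This uses the 20% criterion; the 5 mm minimum governs only when the reference sum is below 5/0.20 = 25 mm.

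| Assumed s | Further fall for irPR | Growth from Day 1 size for irPD at first scan |
|---|---|---|
| 0% | 30.0% | 20.0% |
| 5% | 26.3% | 26.3% |
| 10% | 22.2% | 33.3% |
| 15% | 17.6% | 41.2% |
| 20% | 12.5% | 50.0% |

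For example, at s = 15%, 1 − 70/85 = 17.6% and 120/85 − 1 = 41.2%. Both columns favor study treatment: response is easier to reach, and progression at the first scan is harder to reach. Once a later scan is smaller than baseline, that scan becomes the nadir and the effect on irPD ends.

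**4. Sample size.** The primary design does not use tumor scans. As a check, n = [(1.645 × √(0.45 × 0.55) + 0.842 × √(0.70 × 0.30)) / 0.25]² = 23.2, which rounds up to the plan's 24. This point does not change it.

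**The case against.** The strongest reply is that the effect is bounded, unmeasured and confined to descriptive endpoints. Much of that stands. Response rate and PFS are estimated without a hypothesis test (2.2, 8.3). The arithmetic applies only to patients with measurable disease. Fourteen days is the most the plan allows, not what is expected. Dose Level 1 eligibility, which requires either no available systemic therapy or an acceptable delay in giving it, narrows exposure without excluding it.

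A reader might go further than the documents allow in four ways.

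- **That growth before Day 1 shows the same fault.** Such growth would make irPD easier to reach, but a patient last treated on day −29 and scanned on day −28 can grow untreated for the same four weeks. That is an effect of scan age, and reordering scan and treatment does not remove it.
- **That the plan is silent on confounding therapy.** Exclusion 3.2.11 lets the investigator exclude a patient for a therapy that might confound the results. It is discretionary and sets no order between scan and treatment, so it mitigates the gap without closing it.
- **That lesions irradiated after the scan will be measured as study disease.** Section 6.8 relies on a cited irRECIST source and gives no target-lesion selection rules of its own. That source is not available here, so the point stays open.
- **That the primary result is biased.** It is not. Effusion resolution is judged on drainage volume and symptoms (2.4.1.2).

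What remains is that the plan permits the sequence and that two stated objectives rest on the scan.

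**Conclusion.** The gap is real and of limited reach. A compliant baseline scan can predate up to about 14 days of treatment in the classes named in 3.2.2, and shrinkage from that treatment would count toward the secondary response rate. Under an assumed 5% to 20% shrinkage before Day 1, the further fall needed for irPR drops from 30% to between 26.3% and 12.5%. PFS can be affected too, chiefly through the first on-study scan.

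The conclusion rests on the stated windows and on the absence of any scan-specific ordering rule. The shrinkage range is an assumption, and the documents do not give the share of patients affected, so the total bias cannot be sized. The primary endpoint, the 15-of-24 rule and the sample size stand. The change is worth making because the bias is avoidable and the correction is small.

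**What to change.** In footnote 1 of both tables and in section 6.3, require that baseline tumor imaging be done within 4 weeks before Day 1 **and** after the last dose or fraction of any prior anticancer treatment. Wording it for any prior treatment also covers hormonal therapy, which has no stated washout. The eligibility washouts need not change.

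For patients already enrolled, flag those whose baseline scan predates their last prior treatment, using treatment and scan dates (assumed to be on record). Repeat the response rate and PFS without them as a sensitivity analysis.

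The cost is one condition in three places, a later or repeated baseline scan for patients imaged before their last prior treatment, and one extra analysis. The change removes treatment given after the baseline scan. It does not remove delayed carry-over from the last prior dose or untreated growth between scan and Day 1, and the report should say so.
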